## Recruitment Procedures

---

Describe settings where recruitment will occur

Patients will be recruited from around the general New York City/New York area and will present to the Clinic for Aging, Anxiety, and Mood Disorders.

We will be specifically recruiting via advertisements for patients who feel depressed as well as slowed down physically and mentally. Advertisements will include research flyers and brochures posted around CUMC, NAMI website, Facebook advertisements, advertisements in local newspapers and on radio stations, information posted on departmental websites, flyer mailings, pharmacies, Craigslist, ResearchMatch.com, senior community centers, college campuses, and public talks and events. For direct clinical or research referrals, a clinical staff member known to the patient will approach him/her and raise the possibility of study participation. We would also like to implement Columbia University's RecruitMe website as a recruitment method.

How and by whom will subjects be approached and/or recruited?

Recruitment in the Clinic for Aging, Anxiety, and Mood Disorders (CAAM) comes from clinician referrals, response to advertisements (radio, flyer, newspaper, online participant matching websites, Facebook), patients who have finished or are currently enrolled in other protocols in the CAAM, or word of mouth.

If the patient expresses a potential interest in participating, he/she will then be scheduled for a full evaluation with a study clinician. The nature of the study will be thoroughly reviewed with its risks, benefits, and alternatives to participation, and subjects' questions regarding the study will be answered. Subjects will be notified that they may leave the study at any time. Informed consent will be obtained in a private research office. A study clinician will review study procedures and the consent form with each potential participant. Each individual may take as much time as they like to decide if they do or do not wish to participate. The consent form specifies (and the study coordinator emphasizes) that participation is voluntary and withdrawal after signing consent will not affect future care. Subjects will be given a copy of the consent form, and the original will become part of the clinical record.

How will the study be advertised/publicized?

The study will be advertised/publicized through clinician referrals and advertisements, Columbia's RecruitMe website, Research Match website, Facebook, Clinical Connection website, Craigslist website, newspapers, recruitment flyers/brochures and mass mailers at community and senior centers, radio, the National Alliance on Mental Illness NYC Metro Research Studies Website, mass email campaigns from consumer marketing databases, which are compiled using public information, surveys, subscription information, home owner information, and phone directory information, pharmacies, senior community centers, college campuses, and public talks and events.

All web based recruitment procedures have been previously approved by [name] for all of our approved studies.

Do you have ads/recruitment material requiring review at this time?

Yes

Does this study involve a clinical trial?

Yes

YOU MUST REGISTER AT [ClinicalTrials.gov](https://ClinicalTrials.gov) IMMEDIATELY UPON RECEIPT OF IRB APPROVAL AND **PRIOR TO ENROLLMENT** OF THE FIRST SUBJECT. YOU WILL BE PROVIDED WITH A NCT REGISTRATION NUMBER ON REGISTRATION. PLEASE REVISE THIS SECTION OF THE PROTOCOL SUMMARY FORM TO INCLUDE THE NCT NUMBER AND RE-SUBMIT AS AN AMENDMENT TO THE IRB.

## Concurrent Research Studies

Will subjects in this study participate in or be recruited from other studies?

Yes

Describe concurrent research involvement

Subjects who are currently participating in IRBs #7540, #7289R, #7409, #7360, #7489, and/or #7379 and meet the selection criteria for this study will be offered participation. Only an investigator not directly involved with an eligible subject's care will approach the subject to describe this protocol and have an informed consent discussion.

## Inclusion/Exclusion Criteria

Name the subject group/sub sample

Depressed subjects

Create or insert table to describe the inclusion criteria and methods to ascertain them

Inclusion criteria

1. Age 60 years or older
2. DSM5 diagnosis of Major Depressive Disorder (MDD) or Persistent Depressive Disorder (PDD)
3. Montgomery Asberg Depression Rating Scale Score  $\geq 15$
4. Decreased processing speed or decreased gait speed
5. Capable of providing informed consent and adhering to study procedures

Methods of ascertainment

1. Clinical interview
2. SCID, clinical interview
3. MADRS
4. 1 SD below age-adjusted norms on Digit Symbol Test (processing speed) or average walking speed on 15 foot course  $\leq 1\text{m/s}$  (gait speed)
5. Clinical interview

6. Alternative standard treatments for MDD or PDD have been discussed and the individual agrees to be involved in an experimental treatment

6. Clinical interview

Create or insert table to describe the exclusion criteria and methods to ascertain them

**Exclusion criteria Methods of ascertainment**

1. Diagnosis of Substance Use Disorder (excluding Tobacco Use Disorder) in the past 12 months	1. SCID, clinical interview
2. History of psychosis (except brief psychosis associated with transient medical conditions [e.g., delirium, urinary tract infection, etc], psychotic disorder, mania, or bipolar disorder	2. SCID, clinical interview
3. Primary neurological disorder, including dementia, stroke, Parkinson's disease, or epilepsy	3. Medical history, MMSE. PD will be ruled out by satisfying (1) and (2) and (3 or 4) below: (1) patient gives no history of PD during clinical interview, (2) patient's primary doctor gives no history of PD, (3) there are no signs of PD on physical exam in CAAM (e.g., absence of asymmetric resting tremor, decreased arm swing, soft voice, decreased facial expression, difficulty rising from chair, dystonia), (4) if a patient does have one or more signs of possible PD on exam as per (3), then [name] (study neurologist) will come examine the patient and comment on whether PD can be ruled out or whether PD is possible and patient needs further work up
4. MMSE < 24	4. MMSE
5. MADRS suicide item >4 or other indication of	5. MADRS, clinical judgement, CGI

acute suicidality

6. Current or recent (within the past 2 weeks) treatment with antidepressants, antipsychotics, or mood stabilizers

7. History of hypersensitivity, allergy, or intolerance to L-DOPA

8. Any physical or intellectual disability adversely affecting ability to complete assessments

9. Acute, severe, or unstable medical illness

10. Mobility limiting osteoarthritis of any lower extremity joints, symptomatic lumbar spine disease, or history of joint replacement or spine surgery that limits mobility

11. contraindication to MRI scanning

12. History of significant radioactivity exposure (nuclear medicine studies or occupational

6. Clinical interview

7. Clinical interview

8. Clinical interview

9. Clinical interview, physical exam, medical history

10. Clinical interview, physical exam, medical history

11. MRI Safety Screening Form

12. Clinical interview, medical history

exposure)

**13. Has a medical condition managed with medication and/or device and the managing physician considers the condition and/or its management a contraindication to the research use of L-DOPA in this participant**

**13. Clinical interview, medical history, discussion with participant's clinician**

## **Inclusion/Exclusion Criteria #2**

Name the subject group/sub sample

Never-Depressed Elders

Create or insert table to describe the inclusion criteria and methods to ascertain them

Inclusion criteria

1. Age 60 years or older
2. MADRS < 8
3. Capable of providing informed consent and complying with study procedures

Methods of ascertainment

1. Clinical interview
2. MADRS
3. Clinical interview

Create or insert table to describe the exclusion criteria and methods to ascertain them

Never-Depressed Elders will meet all exclusion criteria specified for Depressed Subjects, plus:

Additional Exclusion criteria

1. Any personal history of DSM5 disorder
2. Family history of MDD in first-degree relative

Methods of ascertainment

1. SCID, clinical interview
2. Clinical interview

## **Waiver of Consent/Authorization**

Indicate if you are requesting any of the following consent waivers

Waiver of consent for use of records that include protected health information (a HIPAA waiver of Authorization)

No

Waiver or alteration of consent

No

Waiver of documentation of consent

No

Waiver of parental consent

No

## **Consent Procedures**

Is eligibility screening for this study conducted under a different IRB protocol?

Yes

Indicate NYSPI IRB #

6395R

Describe Study Consent Procedures

Following clinical evaluation and screening procedures, a study clinician authorized to obtain patient consent will explain the study procedures along with the attendant risks, benefits, and alternatives, including the anticipated outcome of doing nothing. The study clinician will then leave the room while the potential subject reads the consent form and return to answer any questions the subject has. During the consent discussion, individuals will be offered the option to take the consent home to discuss with family and/or physician prior to signing it. Subjects who wish to participate will sign the consent form, while those who do not wish to participate will receive appropriate referrals.

Indicate which of the following are employed as a part of screening or main study consent procedures

Consent Form

## Study Procedures

Describe the procedures required for this study

### Overview

The overarching goal of this project is to characterize the influence of dopaminergic system dysfunction on the clinical presentation of late-life depression (LLD) across multiple Research Domain Criteria (RDoC) domains (Positive Valence Systems, Cognitive Systems, and Sensorimotor Systems) at several levels of analysis (cellular [PET], structure / circuit [MRI], and functional / self-report). This IRB pertains to procedures completed at Columbia/NYSPI. A companion grant in this Collaborative R01 project takes place at Vanderbilt University Medical Center and utilizes similar, but not identical procedures (e.g., the PET scanning at Vanderbilt utilizes a different radiotracer). Thus, we have opted to have separate IRB protocols for this project. At Columbia/NYSPI we will enroll 60 elderly depressed outpatients who exhibit behavioral evidence of dopaminergic dysfunction, defined as either slowed processing speed or slowed gait speed. To disentangle the effects of depression from age-related changes, 30 psychiatrically healthy elders also will complete baseline evaluation. After determination of eligibility, baseline assessments include PET imaging measurements of dopamine synthesis and receptor density, neuromelanin-sensitive MRI measurement of long-term nigrostriatal dopamine transmission, task positive MRI focused on effort-based decision making and reward processing, and a comprehensive psychiatric, neurocognitive, and physical performance evaluation. To examine responsivity of the dopamine system to dopamine supplementation with L-DOPA, the 60 depressed subjects (ONLY) then will be randomized to L-DOPA or placebo for 3 weeks, followed by repeat multimodal MRI, neurocognitive and behavioral assessments. In a cross-over design, participants will then receive the opposite intervention for an additional 3 weeks followed by clinical and cognitive assessments only.

### Evaluation

1. Every subject (both potential Depressed participants and Never-Depressed participants) evaluated for this protocol will receive a clinical interview by a psychiatrist or psychologist. A psychiatrist or other qualified physician will see participants to evaluate medical aspects of eligibility, including screening for signs or symptoms of Parkinson's Disease (PD). If there is any concern, they will be referred to the study neurologist ([name] at Columbia). Additional assessments will be administered by a trained rater (BA, RN, or SW) in CAAM, including the Montgomery Asberg Depression Rating Scale (MADRS) and a SCID performed by a trained rater. Never-Depressed Elders will be selected for participation based on this initial assessment and clinical interview, while potential Depressed subjects will be further assessed as below.
2. If a subject has a diagnosis of Major Depressive Disorder (MDD) or Persistent Depressive Disorder (PDD), he/she will be informed of this and educated about the availability of treatments for depression. If a subject is not interested in depression treatment during the 6-8 weeks of study participation and/or prefers to begin with an experimental treatment for slowing and depression, he/she will be offered participation in the present study provided there is no suicidal ideation present. Based on the extant data supporting the efficacy

---

of antidepressants for MDD and PDD, they will be informed that antidepressant treatment would be a very reasonable option for their condition. These potential subjects will be offered the option of being referred out for depression treatment, and it will be clarified that L-DOPA is not as yet a treatment for MDD. Thus, all potential participants in this study must state their preference not to be treated with a standard treatment for depression.

3. Next, trained raters (BA, RN, or SW) in CAAM will assess processing speed using the Digit Symbol test from the WAIS-III and the Trail-Making Test Part A. Digit Symbol or Trails A will be used as a selection criterion, with patients included in this study if they score 0.5 SD below the age-adjusted norms on Digit Symbol or Trails A. Patients' gait will be assessed by trained raters as walking speed in m/s on a Gaitrite walkway system. Patients are instructed to walk at their usual or normal speed starting and ending at a point 6 feet prior to and after the walkway course to eliminate acceleration and deceleration effects. Two trials will be completed, and gait speed will be based on the average of 2 trials. Gait speed will be used as a selection criterion, with patients included in this study if they have a gait speed < 1 m/s.

4. If subjects are eligible for the study after review of their processing speed and gait speed and decide to participate by signing informed consent, then they will complete the remainder of the baseline assessment. This includes recording of each subject's chief complaint, referral source, age of onset of mood and/or cognitive decline, number prior depressive episodes, age, sex, marital status, race and ethnicity, years of education, employment status and income, years of education, family history. We also will document medical history, physical exam, urine drug screen, CBC, chemistries and electrolytes, thyroid profile, vitamin B12 and folate levels, urine analysis, and ECG. Vital signs will be measured at baseline and monitored weekly throughout the study. The Cumulative Illness Rating Scale-Geriatric (CIRS-G) will be filled out at baseline to measure chronic medical illness burden. Subjects' current physical pain will be assessed weekly using a 100mm Pain Visual Analog Scale (VAS) and used as a covariate in analyses of gait speed.

5. Additional plasma will be separated and pipetted into tubes to be transferred to [name] laboratory at Emory University for measurement of baseline markers of inflammatory status, including C-reactive protein (CRP), IL-6, and Tumor Necrosis Factor  $\alpha$  (TNF $\alpha$ ). The rationale for inflammatory marker measurement is evidence that dopaminergic dysfunction in older adults may be caused by the chronic, low-grade inflammatory process concomitant with aging ("inflammaging"). Pro- inflammatory cytokines such as IL-6 may reduce dopaminergic transmission in multiple ways, including decreasing dopamine synthesis by limiting tetrahydrobiopterin (BH4) availability, impairing vesicular release of dopamine in presynaptic neurons by decreasing expression of vesicular monoamine transporter 2 (VMAT2), increasing DAT reuptake of synaptic neurotransmitter, and decreasing glutamate-dependent dopamine signaling.

**6. In the situation where a potential participant is taking medication and/or has a device to stabilize or manage a medical condition, the research physician will, without exception, contact the physician managing the condition to describe the possible research use of L-DOPA, to discuss any possible risks, and to obtain the managing physician's opinion as to whether the participant's condition and/or its management is a contraindication to the research use of L-DOPA in this participant. This discussion and its outcome will be documented in the research chart.**

**7. Otherwise eligible subjects who are currently taking an ineffective antidepressant medication (i.e., the individual is symptomatic at a level meeting inclusion criteria) will be offered participation as above after a discussion of the risks, benefits, and alternatives. No patients will be taken off of effective antidepressant medications solely for the purpose of research. Should an individual taking an ineffective antidepressant medication wish to participate and sign consent, their psychiatric care will be taken over by a CAAM study clinician after a discussion with their prescribing physician. Such participants will be tapered off of the ineffective medication as per standard clinical practice (depending on the medication) and be followed closely in CAAM, likely through weekly visits. Should a participant be unable to tolerate the medication taper due to increasing depressive symptoms, they will be withdrawn from the study and entered into the 3 month open treatment period directly. Once participants are washed off of the medication they will proceed with the study assessment described in points 8-10 immediately below. Subjects must be off medication for 2 weeks prior to neuroimaging procedures and beginning the L-DOPA study medication.**

**8. Other neuropsychological measures completed at baseline include trained study rater (BA, RN, SW) assessment of processing speed using the Pattern and Letter Comparison Tests, broad cognitive evaluation with the NIH Toolbox, and evaluation of executive function via the NIH-EXAMINER battery designed to assess executive functions reliably, comprehensively, and efficiently (154-155). This battery examines working memory, inhibition, set shifting, fluency, insight, planning, social cognition and behavior. We also include the supplemental NIH Toolbox Auditory Verbal Learning (Rey) Test for a robust assessment of episodic memory and allow for classification of amnestic mild cognitive impairment.**

**9. Domains of function assessed by trained study raters (BA, RN, SW) at baseline include: the Short Physical Performance Battery (SPPB), a performance measure of gait, balance, and lower extremity strength sensitive to meaningful change. The 36-item self-report World Health Organization Disability Assessment Schedule 2.0 (WHODAS2) provides a global measure of disability and 7 domain-specific scores based on the conceptual framework of the International Classification of Functioning, Disability, and Health (ICF). The Falls Efficacy Scale-International will assess subjects' fear of falling weekly using a 16-item scale rating respondents' confidence (1 not at all concerned—4 very concerned) in doing daily tasks without falling.**

**10. Finally, additional clinical measures include the Antidepressant History Form (ATHF), the Daily Inventory of Stressful Events, the Perceived Stress Scale, and the Duke Social Support Index. Depressive symptoms will be measured with the MADRS in addition to the Inventory of Depressive Symptoms--Self Report (IDS-SR).**

### **MRI Scanning**

**11. All of the N=60 Depressed subjects and N=30 Never-Depressed subjects will undergo neuroimaging, but the Depressed subjects will undergo a pre-treatment MRI and a post-treatment MRI following Step 1 (3 week duration) of the LDOPA study, whereas Never-Depressed Elders will have a baseline scan only (because they will not participate in below LDOPA study). MRI and PET scanning (see below) may occur on the same day if this can be scheduled (MRI occurring first, followed by PET scan). However, due to the tightness of scheduling for these scanners, it is more likely that the MRI and PET scans will occur on**

---

different days--one day for MRI scan and one day for the PET scan. Typically the MRI scanning day will come before the PET scanning day.

12. MRI of the brain will be acquired using a GE Premier 3.0T System. For PET / fMRI coregistration and region of interest determination we will use a sagittal, whole-brain T1-weighted 3D sequence (MPRAGE) with TR/TI/TE = 2400/ 1000/ 2.22ms, flip angle (FA) 8, field of view (FOV) 240x256, 0.8mm isotropic resolution (no slice gap), and parallel imaging acceleration factor of 2 (Philips SENSE, GE ARC/ASSET). For assessment of white matter hyperintensities (WMH) we will use an axial, whole-brain T2 FLAIR sequence with TR/TI/TE = 9690/2500/91ms, FA 136, FOV 240x256, 0.8x0.8x1.6mm resolution (no slice gap), and parallel acceleration factor of 2.

13. For the BOLD functional MRI, we will use an axial, whole-brain gradient-echo echoplanar imaging (EPI) sequence: TR/TE = 1000/30ms, FA 45, FOV 220x220, 2.3mm isotropic resolution (no slice gap). Multiband and parallel imaging acceleration factors will be tuned for each scanner to obtain the specified TR/TE/voxel size. The most inferior functional slice will be inferior to the most inferior aspect of the temporal lobes. Prior to functional image acquisition, an axial, whole-brain field map is collected to correct for distortions caused by magnetic field inhomogeneities with TR/TE1/TE2 = 590/4.92/ 7.38ms, FA 60, FOV 220x220, 2.3mm isotropic resolution. We will also collect a pair of single volume spin-echo EPI with opposite phase encoding direction to provide an alternative method for field map computation.

14. Two tasks will be undertaken in the scanner. The first is the Effort Expenditure for Rewards task (EEfRT). On each EEfRT trial, participants decide whether to work harder for a larger reward (high number of finger presses with their pinky), or expend less energy (low number of presses with a dominant index finger) for a lesser reward, with lower rewards being \$1 dollar and higher rewards ranging from \$1.20 to \$5. Participants receive information about the probability of winning on each trial regardless of their pick and one trial from each run is randomly selected for payout. Computational modelling of the EEfRT allows an estimation of the effort level at which people begin to discount rewards, and the rate of discounting once they start discounting. Because these models are more accurate with at least 3 levels of effort, the modified EEfRT offers subjects choices between high and low effort, low and medium effort, and medium and high effort (one third of trials each). The level of effort is manipulated using the number of finger presses and which finger on the nondominant or dominant hand is utilized. The number of button presses (required in a 10s response window) will be calculated as a percentage of each participant's maximum sustained button press rate in order to control for differences in ability level. The response rate (20% index dominant, 50% middle finger nondominant, 80% pinky nondominant) and time span for the responses have been calibrated for this population in order to limit floor effects seen in some participants in past EEfRT studies. Participants will complete three 320-s runs for a total of 60 trials. The following equation will be fit to the data utilizing in-house computational modelling scripts in MATLAB:  $SV = M - kCp$ , where SV= subjective value, M = monetary value of the chosen reward, k= the discount rate, C = the effort level of the option, and p determines the inflection point at which participants begin to discount. We will further examine traditional measures of the proportion of high-effort choices made during the session (primary outcome), and the relative influence of reward magnitude on making a high-effort choices (reward magnitude beta derived from a generalized estimating equation (GEE), as a weakening of reward magnitude sensitivity in decision making has been seen in our past studies with depressed patients .

15. The second task is the Monetary Incentive Delay task (MIDT). On each trial, participants are presented with a 2000msec cue indicating that trial's reward value (\$0, \$1, or \$5). After the cue, a 2000-2500 msec delay period ensues as the participant waits for the target. Participants press a button as quickly as possible when the target is visible. After another delay lasting from 950 to 2800 msec, a feedback screen lasting 2500msec appears indicating the outcome ("Hit!" or "Miss!") for each trial, with a brief ISI before the next trial and an average trial length of 8 s. Target duration is continually adjusted during the session based on individual performance to keep success rate at 60%. Participants will complete 96 trials over three five-minute runs, for a total of 32 trials with each cue. Participants receive the money they win from the run with the greatest earnings. We include only gain trials to maximize the number of trials per condition to improve statistical power. This task distinguishes between reward anticipation and notification of reward receipt, and for modeling responses to the presence or absence of reward and responses to the magnitude of rewards. Modeling will use our past approach with the primary contrast being reward anticipation (Potential Win Anticipation > No Change Anticipation) and secondarily reward response (contrast Win Feedback > No Change Feedback). Post-hoc tests will examine the relationship between discounting behavior by reward magnitude and BOLD signal, contrasting responses to the three reward values (\$0, \$1, or \$5).

16. Finally, neuromelanin-sensitive MRI (NM-MRI) will be conducted, which has been successfully implemented by Co-Inv [name] at NYSPI in several studies. NM-MRI consists of 2D gradient echo (GRE) images with magnetization transfer (MT) contrast of the midbrain (2D-GRE-MT, 0.39 mm^2 in-plane resolution, 1.5mm slice thickness, 20 slices, FOV=162×200 mm, FA=40°, TR= 260 ms, TE=2.68 ms, MT frequency offset=1200 Hz, AC-PC alignment). To ensure imaging of the substantia nigra (SN), the image stack will be manually positioned by trained research staff according to anatomical landmarks on the high-resolution T1w scan, a protocol that yields excellent test-retest reliability for voxelwise analysis (median ICC=0.91).

17. For all of the MRI procedures, participants are instructed to lie as still as possible within the magnet. The MRI scan is completed in one session, and lasts for a total of approximately 90 minutes, including time for positioning subjects in the scanner. All precautions and protections are given to the participant to ensure that they are as safe and as comfortable as possible. For participants' comfort within the scanner, they lie on a padded table with a pillow to rest their heads on. A blanket is also provided to keep participants warm during the procedure. If the participant appears nervous or anxious, a trained member of the research staff remains with them inside the scanning suite for the duration of the scan. The participant is given a squeeze ball to terminate the scan at any time. If he/she squeezes the ball, he/she will be removed from the scanner immediately. Participants may decline the MRI scans at any time. If the participant chooses not to be scanned, his/her participation in the study will not be affected. Of course, a structural MRI scan would be required to participate in the PET scans. Any subject who cannot have at least a structural MRI scan would not be able to participate in this protocol. All of the MRI procedures are conducted on the 3-Tesla MRI scanner at the New York State Psychiatric Institute. Conducting these procedures will be an accredited Magnetic Resonance Technologist and one member of the research staff (Bachelor's Level or Higher), or [name] or [name], present.

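### The effort-discounting model in protocol item 14 has no onset or inflection point, so its parameters p and k cannot be read as where discounting starts and how fast it then runs

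*Protocol*

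**What the plan says.** Item 14 of the protocol's MRI Scanning section describes the EEfRT and says that computational modelling gives "an estimation of the effort level at which people begin to discount rewards, and the rate of discounting once they start discounting". It then commits to fitting one equation with in-house MATLAB scripts, printed as SV = M − kCp. M is the monetary value and the other terms are defined as "k= the discount rate, C = the effort level of the option"; of the last parameter it says that "p determines the inflection point at which participants begin to discount". Neither document gives another form of the equation, a threshold term or a sigmoid.

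Three effort levels are used, set as a share of each person's maximum press rate: "20% index dominant, 50% middle finger nondominant, 80% pinky nondominant". All three pairings are offered, one third of trials each ("Participants will complete three 320-s runs for a total of 60 trials"). The number entered for C (0.2, 20 or 1, for example) is not stated.

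The same item says that the team will also examine "traditional measures of the proportion of high-effort choices made during the session (primary outcome") and a reward-magnitude coefficient from a GEE. The SAP, under Aim 1 Hyp 1, lists the high-effort proportion, the influence of reward magnitude and ROI activations; under Hyp 3 it uses the probability of choosing the high-effort option. It names neither k nor p.

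**The concern.** The protocol attributes to the model two separate outputs: when effort starts to count, and how steeply it counts after that. A model can return these only if it contains a starting point and a slope beyond it. The printed equation appears to contain neither.

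What is at stake is interpretation. The protocol's integrative model (section A.7) holds that slowing raises effort costs and so lowers motivation. Of the EEfRT measures, k and p are the only ones presented as separating onset from steepness. If a paper reported that depressed participants, or participants on L-DOPA, differed in onset because p differed, or in rate because k differed, the fitted model would not bear that out.

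**Working it through.** **Inputs.** From item 14: the equation, the stated roles of k and p, and effort levels of 20%, 50% and 80% of maximum press rate. Assumed here: the equation is a power, SV = M − kC^p; C is coded 0.2/0.5/0.8 unless noted; and, for the illustration only, people have zero cost up to an onset and then a linear cost. The documents print no figure for k or p, so there is nothing to reproduce first.

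**1. Is there an inflection?** The second derivative of SV in C is −kp(p−1)C^(p−2). For fixed k and p its sign is the same at every C > 0, and at p = 1 it is zero throughout. A numerical scan over C in (0, 1] for p = 0.3, 0.5, 1.5, 2, 3, 5 and 10 found no sign change. There is no inflection.

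**2. Is there an onset?** With k > 0, kC^p is above zero at every C > 0, whatever p is. One could define a start as the effort at which cost reaches some amount e, which gives C = (e/k)^(1/p). That needs k and an arbitrary e as well as p. For e = $0.10 and p = 3:
- k = 1: C = 0.1^(1/3) = 0.464
- k = 2: C = 0.05^(1/3) = 0.368

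The same p gives two different starts.

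**3. Is k a rate?** The local slope of the cost is kpC^(p−1), which equals k at all efforts only if p = 1. With k = 2, the slopes at C = 0.2, 0.5 and 0.8 are:
- p = 1: 2, 2, 2
- p = 3: 6 × 0.04 = 0.24, 6 × 0.25 = 1.5, 6 × 0.64 = 3.84

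k is the cost at C = 1. Recoding C in percent turns k into k/100^p. At p = 2, k = 2 becomes 0.0002 with identical predicted choices.

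**4. What would the fit return if people did have an onset?** Choices depend on cost differences between the two options, so the three levels supply two numbers: d1 (medium over low) and d2 (high over medium). The low–high pairing gives only their sum. Take a slope of $4 per unit effort after the onset for everyone. Solve (0.8^p − 0.5^p)/(0.5^p − 0.2^p) = d2/d1 for p, then k = d1/(0.5^p − 0.2^p).

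| True onset | d1 | d2 | d2/d1 | p | k |
|---|---|---|---|---|---|
| 0.2 | 4 × 0.3 = 1.20 | 1.20 | 1.0 | 1.00 | 4.00 |
| 0.3 | 4 × 0.2 = 0.80 | 1.20 | 1.5 | 1.65 | 3.22 |
| 0.4 | 4 × 0.1 = 0.40 | 1.20 | 3.0 | 2.83 | 3.07 |

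Check for the last row at unrounded p (2.826): 0.8^p = 0.5322, 0.5^p = 0.1410, 0.2^p = 0.0106. The differences are 0.3912 and 0.1304, their ratio is 3.00, and k = 0.40/0.1304 = 3.07.

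The slope is 4 in every row, yet k falls by 1 − 3.07/4.00 = 23% as the onset moves from 0.2 to 0.4. p rises with onset but never equals it. The columns d1 and d2 are what the choices identify, and they do not depend on the coding of C.

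**The case against.** The strongest reply concerns consequence. Item 14 names the high-effort proportion as primary, and no test in the SAP names k or p. A reader might infer that the effort results of Aim 1 or Aim 2 are compromised. The documents do not support that, and this objection stands in full.

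Second, the protocol says that p determines the point, not that p is an effort level, and p does rise with onset in the table. That stands in part: a larger p loosely means that cost becomes noticeable later. As step 2 shows, though, p does not fix any such point without k and an arbitrary threshold.

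Third, the 23% comes from assumed discounters. Nothing in the documents says that participants behave that way or gives the slope. It illustrates direction and rough size and is not a forecast.

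Three stronger readings are tempting and should not be drawn:
- **A literal product.** Taken as k × C × p, the equation could not separate k from p. A superscript lost in reading the PDF is the likelier explanation, so nothing here rests on the product.
- **Rank reversal.** Two people can swap order on k between proportion and percent coding. One analysis uses one coding for everyone, so this shows only that the coding must be stated.
- **A sigmoid cost as the remedy.** Its turning point is half-maximum, not onset. With a free ceiling it has three parameters for two cost differences. For the onset-0.4 person above, ceilings of $2.50, $3, $5 and $8 all fit exactly, with turning points 0.70, 0.76, 0.93 and 1.09.

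**Conclusion.** The point holds as a mislabelled secondary model. Under the power reading, the absence of an inflection and an onset follows from the algebra and needs no assumption about behaviour. p is curvature; k is a scale that depends on p and on an unstated coding of C. Neither can support a claim about where discounting starts or how fast it runs afterwards. The size given (k lower by 23% for an onset of 0.4 against 0.2 at equal slope) rests on the onset-then-linear assumption and on the 0.2/0.5/0.8 coding. Severity is minor, because the primary EEfRT outcome and the tests named in the SAP are unaffected. The in-house scripts are not part of the documents, so this concerns the model as written.

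**What to change.** In protocol item 14:

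1. Keep the cost term and print it unambiguously as kC^p.
2. Label p as curvature and k as scale.
3. State that C is the proportion of maximum press rate, coded 0.2, 0.5 and 0.8.
4. Remove the statements that the model estimates the effort at which discounting begins and the rate after that.
5. Base any group or L-DOPA comparison from this model on the two identified dollar costs: k(0.5^p − 0.2^p) for medium over low effort, and k(0.8^p − 0.5^p) for high over medium.

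The cost is a change of wording and a few lines in the script that convert fitted k and p to the two dollar amounts. No new data are needed. The price is that onset is no longer claimed.
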